5.5.1 Adverse events

All AEs will be coded using the latest version of MedDRA at the time of the database lock. The actual version of the MedDRA coding dictionary used will be noted in the AE tables and listings.

Treatment-emergent adverse events (TEAEs) are defined as adverse events that occur or worsen on or after the first dose of study treatment.

The severity of the adverse events is assessed by the investigator as mild, moderate, or severe. The relationship to the study drug is determined by the investigator as definite, probably, possibly, unlikely, or unrelated. The categories "unrelated" and "unlikely" will be mapped to "unrelated", the categories "possibly", "probably" and "definite" will be mapped to "related".

An adverse event is considered a serious adverse event (SAE) if it results in any of the following outcomes: 1) results in death, 2) is a life-threatening adverse event, 3) requires hospitalization or prolongation of existing hospitalization, 4) results in a persistent or significant disability/incapacity or substantial disruption of the ability to conduct normal life functions, or 5) a congenital anomaly/birth defect.

An overall summary of TEAEs will be presented showing the number and percentage of participants with: any TEAE, any study drug-related TEAE, any severe TEAE, any treatment-emergent SAE, any study drug-related treatment-emergent SAE, any TEAE leading to study discontinuation, and any TEAE leading to death.

The following TEAEs will be summarized as frequency and percentage of participants by SOC and PT:

- TEAEs
- TEAEs by descending PT
- Severe TEAEs
- Study drug-related TEAEs
- Treatment-emergent SAE
- Study drug-related treatment-emergent SAE
- TEAEs leading to study discontinuation

All adverse events for each patient, including the same event on multiple occasions, will be listed, indicating the preferred term.

Drug-related TEAEs will be analysed using ordinal logistic regression with the untoward effect classified as absent, mild, moderate, or severe and the factorial treatment regimens (without interaction term) as predictor variables. For a count outcome such as the number of TEAEs or treatment-emergent SAEs incidence rate ratio (IRR) and its 95% CI will be computed using Poisson or Negative binomial regression.

The following by-participant listings will be provided:

- AEs
- SAEs
- TEAEs leading to study drug withdrawal
- TEAEs leading to study drug interruption
- TEAEs leading to study discontinuation

• TEAEs leading to death

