# **Blinding**

All samples sent to the laboratory for analysis will be coded to ensure a blinded assessment of the efficacy outcomes. Participants and the study investigators assessing drug safety will not be blinded for treatment arms.

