# 8.3.3.2 RELATIONSHIP TO STUDY INTERVENTION

The Site PI or delegated study physician at each site must assess the relationship between investigational product (study drug) and each AE/SAE. The study physician will use clinical judgment to determine the relationship. Alternative causes, such as natural history of the underlying diseases, concomitant therapy, other risk factors, and the temporal relationship of the event to the investigational product will be considered.

The degree of certainty about causality will be graded using the categories below.

Version 4.0

ALIVE Study 21st January 2022

Definite: The adverse event has a strong temporal relationship to study drug and/or recurs on re-

challenge, and cannot be explained by an alternative aetiology.

Probably: The adverse event has a strong temporal relationship to study drug or recurs on re-challenge,

and an alternative aetiology is unlikely or significantly less likely.

Possibly: The adverse event has a strong temporal relationship to the study drug, and an alternative

aetiology is equally or less likely compared to the potential relationship to study drug. The

alternate aetiology should be provided by the investigator.

Unlikely: The adverse event has little or no temporal relationship to the study drug and/or a more

likely alternative aetiology exists. The alternate aetiology should be provided by the

investigator.

Unrelated: The adverse event is due to underlying or concurrent illness or effect of another drug and is

not related to the study drug. The alternate aetiology should be provided by the investigator.

The categories "unrelated" and "unlikely" will be mapped to "unrelated", the categories "possible", "probable" and "definite" will be mapped to "related".

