#### 9.5.4 SAFETY ANALYSES

For the safety analysis in phase III, the ITT (those participants who have received at least one dose of study intervention) will be used for the analysis and participants will be considered by arm and by both FDC arms pooled (overall) and by number of doses of FDC received to explore dose-responses. Drug-related AEs will be analysed using ordinal logistic regression with the untoward effect classified as absent, mild,

Version 4.0

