5.1.5 Handling of missing data

Every effort will be made to minimise the amount of missing data in the trial. Information on the reason for missing data will be obtained, whenever possible.

Baseline demographic data

For missing data on age, gender, height and weight at baseline, multiple imputation will be performed. **Efficacy data**

For the efficacy analysis, the worst-case scenario will be considered, where participants with missing data will be considered as treatment failures. In such a case it will be assumed that all participants with no egg count data at day 21 will have the same egg count as at baseline.

Adverse Events

The following imputation rules for missing or partial AE start dates are used:

- If only Day is missing, the start day will be the first day of the month or the date of study drug first dose if the AE end date is on/after the date of study drug first dose or is missing/partial AND the start year and month of the AE are the same as year and month of the study drug first dose date;
- If Day and Month are both missing, the start date will be January 1 of the year or the date of study drug first dose if the AE end date is on/after the date of study drug first dose or is missing/partial AND the start year of the AE is the same as year of the study drug first dose date;
- If Day, Month, and Year are all missing, the date will not be imputed. However, if the AE end date is on/after the date of study drug first dose, then the AE will be considered a TEAE.

The missing or partial AE stop data will not be imputed.

If the severity of an AE is missing, it will be classified as "severe" in the summary tables by severity. If the assessment of relationship of study drug is missing, it will be classified as "related" to the study drug.

Concomitant Medications

The same imputation rule as AE start date imputation will be used for missing or partial start dates of medications.

The missing or partial medication stop data will not be imputed.

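### The only severity model is limited to events that an unblinded physician calls drug-related, so attribution alone could create or hide a between-arm severity difference; no all-cause severity model is planned

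*SAP*

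**What the plan says.** **The severity model.** SAP 5.5.1: "Drug-related TEAEs will be analysed using ordinal logistic regression with the untoward effect classified as absent, mild, moderate, or severe". Protocol 9.5.4 has the same model, also for drug-related events: "AEs will be analysed using ordinal logistic regression with the untoward effect classified as absent, mild" and upwards. No other model in either document uses severity.

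**How an event becomes drug-related.** Protocol 8.3.3.2: "The study physician will use clinical judgment to determine the relationship". There are five categories. Possibly, probably and definite are mapped to related; unlikely and unrelated are mapped to unrelated. Where the assessment is missing, SAP 5.1.5 applies one rule to all arms: "If the assessment of relationship of study drug is missing, it will be classified as 'related' to the study drug".

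**Who judges.** Protocol 6.3, Blinding: "Participants and the study investigators assessing drug safety will not be blinded for treatment arms". Blinding covers the coded laboratory samples only. No blinded causality review is described.

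**What is planned regardless of cause.** SAP 5.5.1 has a rate model ("For a count outcome such as the number of TEAEs or treatment-emergent SAEs incidence rate ratio (IRR) and its 95% CI") that does not use grade. It also has a summary of participants with "any TEAE, any study drug-related TEAE, any severe TEAE, any treatment-emergent SAE" and further categories, and tables by SOC and PT for all TEAEs and for severe TEAEs. These summaries and tables are descriptive.

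**The endpoint.** The Phase II primary and Phase III secondary safety endpoints name frequency, type, severity and relationship to study drug, for all adverse events.

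**The concern.** Relationship and severity are separate attributes in the endpoint. The model turns the first into a filter on the second, and an unblinded assessor applies the filter. The cut falls between possibly (an alternative cause is equally or less likely) and unlikely (an alternative is more likely), which is a fine distinction for non-specific complaints. Protocol 2.2 reports headache and abdominal pain as the most frequent events in the earlier Honduras trial. The same headache may be called possibly related after the investigational tablet and unlikely after the familiar control. It then counts in one arm and is absent in the other. Randomisation does not protect against this, because the judgement is made after allocation.

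Part of the problem needs no prejudice. The possibly category requires a strong temporal relationship to the drug. The three-day arm is dosed on Days 0, 1 and 2, the other two arms on Day 0 only. An incidental headache on Day 2 can fall within hours of a dose in one arm and two days after the only dose in the others. A fair assessor could classify it differently.

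At stake is the one modelled comparison of severity between arms. It could show a difference that does not exist or miss one that does.

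**Working it through.** The documents state no figure for this model, so there is none to reproduce. The check asks how large a spurious difference could be when nothing but attribution differs.

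**Inputs from the documents**
- ALB 251 and one FDC arm 419 in Phase III (SAP 3.5). The text gives FDC 427 and FDCx3 419. Table 4 sums the other way: FDCx1 198 + 120 + 101 = 419 and FDCx3 198 + 119 + 110 = 427. ALB is 103 + 47 + 101 = 251 in both. The swap hardly matters here (see Sensitivity).
- Two-sided 0.05 (SAP 5.7).

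**Assumptions (not in the documents)**
- True TEAE incidence r, equal in both arms: 10%, 20% or 30%.
- Share of events called related: 50% after ALB; a = 60%, 70% or 80% after FDC.

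**Formulas**, for a binary test of any related event:
- p1 = 0.5r and p2 = a·r
- odds ratio = [p2/(1−p2)] / [p1/(1−p1)]
- P(false FDC-worse) = Φ{[(p2−p1) − 1.96·s0]/s1}, where s0 = √[p̄(1−p̄)(1/251 + 1/419)], s1 = √[p1(1−p1)/251 + p2(1−p2)/419] and p̄ is the pooled proportion

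**One case in full** (r = 30%, a = 80%): p1 = 0.15, p2 = 0.24, odds ratio 1.79, p̄ = 0.2063, s0 = 0.0323, s1 = 0.0307. Then (0.09 − 1.96 × 0.0323)/0.0307 = 0.87, and Φ(0.87) = 0.808.

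**All cases** (odds ratio; probability of a false FDC-worse result, nominal 2.5%)

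| True incidence | a = 60% | a = 70% | a = 80% |
|---|---|---|---|
| 10% | 1.21; 7.4% | 1.43; 16.8% | 1.65; 30.8% |
| 20% | 1.23; 11.7% | 1.47; 32.2% | 1.71; 59.3% |
| 30% | 1.24; 16.5% | 1.51; 48.6% | 1.79; 80.8% |

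**Sensitivity**
- Using 427 in place of 419 moves no entry by more than 0.3 percentage points.
- Protocol 4.2 counts a child with mixed infection once for each species, so distinct children may be fewer than 251 and 419. With 20% fewer (assumed; 201 and 335), 80.8% becomes about 71% and 16.5% about 14%.

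**Does the binary test stand in for the ordinal model?** The score test of the proportional-odds model was simulated (20,000 trials per scenario, ALB 251 against both FDC arms pooled, 846). The assumed severity split was 85% mild, 14% moderate and 1% severe, guided by the 85% and 15% that protocol 2.2 reports for the Honduras trial. At 50% against 60% attribution, the rejection rates for 10%, 20% and 30% incidence were 0.077, 0.129 and 0.188. The binary formula at the same sizes gives 0.077, 0.128 and 0.186, so it is an adequate proxy. Run on all-cause severity, the same ordinal test rejected in 0.047 to 0.051 of trials in every Phase III scenario, against a nominal two-sided 0.05.

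**Phase II.** With 26 against 100, the related-only test rejected in 0.01 to 0.26 of simulated trials, with attribution gaps as wide as 30% against 70%. The exposure is mainly in Phase III.

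**The other direction.** Suppose true incidence is 20% after ALB and 30% after FDC, with 60% and 40% called related (assumed). The related rates are 0.20 × 0.60 = 0.12 and 0.30 × 0.40 = 0.12. A real excess disappears from the drug-related data.

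**The case against.** **All-cause severity is not absent from the report.** A reader might infer that severity is seen only through related events. The documents do not support that. All-cause TEAEs and all-cause severe TEAEs are both tabulated, and TEAEs are modelled as counts. Equal all-cause incidence beside unequal related incidence would be visible. This objection stands and narrows the gap to the missing all-cause model on the graded scale.

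**Relationship is part of the endpoint.** A model of related events answers a legitimate question about adverse reactions. Causality has defined categories, and the assessor must state an alternative cause for possibly, unlikely and unrelated. This supports keeping the drug-related model. It does not supply a severity comparison for all adverse events, which the endpoint also covers.

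**No decision rests on the model.** A reader might infer that a wrong safety decision could follow. The stated hypotheses (protocol 9.1, SAP 5.3.1) concern efficacy. The suspension and progression rules count serious adverse reactions or SUSARs and lead to DSMB review; they do not use this model. That stands.

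**The rates are assumed.** This stands too. The upper figures depend on 30% incidence and a wide attribution gap. They illustrate exposure and do not predict an error rate. Over-attribution to FDC is also only one direction, and it works against the new product.

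**An all-cause model is not unbiased.** Severity is graded by the same unblinded physician. The 3-hour post-dose observation is repeated on Days 1 and 2 in the three-day arm only, so events may be detected more readily there. Both limits remain after the change.

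**Conclusion.** The point holds as a modest one. The only model of severity is restricted by a judgement that unblinded physicians make, and the plan has no all-cause counterpart on the mild, moderate, severe scale. Differential attribution could therefore create or hide a between-arm difference in that model.

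Its size cannot be known from the documents. Under the stated assumptions the probability of a false FDC-worse result runs from 7.4% to 80.8% against a nominal 2.5%. The lower end goes with 10% incidence and a 10-point attribution gap, the upper end with 30% incidence and a 30-point gap. The figures are somewhat lower if co-infection reduces the number of distinct children.

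The documents do not support reading this as bias in a known direction or as a threat to a trial decision. The rule that sets missing relatedness to related does not remove the problem, which lies in relatedness that was actually judged. The case for change is that the correction is specific and nearly free.

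**What to change.** In SAP 5.5.1 and protocol 9.5.4, specify the same ordinal logistic model for each child's worst severity over all TEAEs, regardless of relationship, with children who had no TEAE classed as absent. Report it as the main modelled severity comparison, by arm and with the FDC arms pooled, as already planned for safety. Keep the drug-related model as supportive and show the two side by side.

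State the remaining limits in the SAP: severity grading is unblinded, and the three-day arm has extra post-dose observation.

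The cost is a change of wording and one more run of a planned model, since severity is recorded for every adverse event. The statistical price is some dilution by incidental events unrelated to treatment.

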#### **Primary outcome measures**

Safety evaluations: Safety evaluations and measurements, including adverse events, vital signs, physical examination, weight, height and BMI will be assessed after signing the informed consent through to post-treatment follow-up visit. To evaluate safety, participants will be evaluated as detailed in the SOA. All adverse events during all study visits, will be noted in the source documents for each participant. A close surveillance, 3 hours post-treatment, will be conducted each day a participant receives study treatment. Any clinically significant abnormalities persisting at the end of the study will be followed up by the study physician until resolution or until a clinically stable endpoint is reached.

A Data Safety Monitoring Board (DSMB) will monitor the ongoing safety of the participants during the study. The following stopping rules will apply at relevant key instances in the ALIVE study:

- The occurrence of ≥1 serious adverse reaction (where causality is at least possible) or SUSAR in any of the weight groups in the Phase II will result in suspension of dose escalation in the FDC arm pending review by the DSMB (keeping in mind the sequential recruitment strategy in phase II).
- The occurrence of ≥2 serious adverse reactions or SUSARs at the end of phase II will result in suspension of progress to phase III pending review by the DSMB.

Overall the occurrence of serious adverse reactions or SUSARs in 2% of the study populations at interim analysis (50% recruitment) will result in suspension of further dosing of the Investigational Product

Version 4.0

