**Treatment allocation** 

Following the completion of all baseline procedures, the participants who fulfil all the eligibility criteria and who have given written informed consent will be allocated to one of the three treatment arms as described in section 4.1.

Post-treatment Phase (Follow-Up)

The study Site Principal Investigator (PI) or delegated study physician will observe each participant for 3h after drug administration. Safety assessment of participants will occur from day 0 (visit 1) to day 3 (visit 4). An additional safety visit will be done at day 7 (visit 5) for follow and monitoring of adverse events. On Day 21 (+/- 7 days) post treatment, a stool collection kit will be provided to each participant for stool collection to be analysed in the laboratory. All assessments for this final visit will be performed as in the SOAs. Visit 6 (Day 21 +/-7days) will be the end of study visit. All participants with a positive STH infection by microscopy on visit 6 (Day 21 +/- 7days) will be provided with rescue treatment. Participants with *S. stercoralis* will be offered ivermectin and participants with *A. lumbricoides*, hookworms and/or *T. trichiura* will be offered albendazole through their local health centres for.

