#### 8.3.7 PREGNANCY

Participants who are ≥12 years old (or post menarche) must have a negative urine pregnancy test to be enrolled into the study. No further pregnancy test will be performed. The duration of the study is 21 (+/-7days). Female participants ≥12 years old will be advised against pregnancy.

In the unlikely event of pregnancy during the trial, pregnancy must be reported to the Sponsor Pharmacovigilance team ([contact]) by the Site PI or delegated study physician within 24 hours of the site becoming aware of it, using a study Pregnancy notification form located in the Investigator's Folder. The investigator must follow up on pregnancies discovered after IP administration until delivery and document the outcome on a new *Pregnancy notification form*, clearly marked as follow-up report. The event fulfils the criterion for an SAE in case of a congenital anomaly (birth defect), foetus death or spontaneous abortion, or adverse events in the neonate that are classified as serious.

Version 4.0 21st January 2022

ALIVE Study

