2.2 Outcomes

2.2.1 Primary outcome

Safety evaluations: Safety evaluations and measurements, including adverse events (AEs), vital signs, physical examination, weight, height and BMI will be assessed from the time of signing the informed consent through to post-treatment follow-up visit. To evaluate safety, participants will be evaluated as detailed in the schedule of visits (Table 1 and Table 2). All AEs during all study visits, will be noted in the CRF for each participant. A close surveillance, 3 hours post-treatment, will be conducted each day a participant receives treatment.

Any clinically significant abnormalities persisting at the end of the study will be followed up by the study physician until resolution or until a clinically stable endpoint is reached.

A Data Safety Monitoring Board (DSMB) will monitor the ongoing safety of the participants during the study.

Efficacy evaluation: Anti-helminthic primary efficacy, measured by cure rate will be determined by analysing a stool sample taken 21(+/-7) days after completing treatment with Kato Katz, Baermann. [1,2]

Cure is defined as absence of the species of STH in participants who had a positive egg count and/or larva for that STH species at baseline. Cure rate (CR) is defined as the proportion of individuals cured (absence of any egg and/or larva) to the total of those infected at baseline with each particular species of STH.

Table 1. Schedule of Activities Phase II Component (KENYA only)

	1							r	
Procedures	Study Visit 0 Screening Day -7 to -1	Study Visit 1 Enrolment/ Baseline Day 0	Study Visit 2 Day 1	Study Visit 3 Day 2	Study Visit 4 Day 3	Study Visit 5 Day 7	Study Visit 6 Day 21+/-7 day post treatment	Unscheduled	Withdrawal
Informed consent ¹	Х								
Informed assent ²	Х								
Stool collection kit delivered	Х						Х		
Stool collection ³	Х						Х		Х
Stool analysis (Baermann and Kato-Katz) ⁴	х						Х		х
Inclusion and Exclusion criteria	Х	Х							
Demographics ⁵	Х								
Physical exam ⁶	Х	Х					Х	Х	Х
Vital signs ⁷	Х	Х	Х	Х	Х	Х	Х	Х	Х
Height	Х	Х							
Weight	Х	Х							
Urine Pregnancy test ⁸	Х								
Haematuria strip test as proxy for Schistosoma h	х								
Randomization and treatment assignation		х							
Study drug administration		X ⁹	X ¹⁰	¹¹ X					
Acceptability questionnaire Arm 1 (ALB)									
Acceptability questionnaire Arm 2 (FDCx1)		х							
Acceptability questionnaire Arm (FDCx3)				х					
PK blood sampling		X ¹²	XI	XI					
Study drug accountability		Х	Х	Х			Х		Х

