2.2.2 Secondary outcomes

Treatment efficacy: Anti-helminthic efficacy, measured through egg reduction rate (ERR), will be determined by analysing a stool sample taken 21(+/-7) days after completing treatment with Kato Katz[2]. Egg reduction rate (ERR) will be calculated by using geometric means, calculated for hookworms, *T. trichiura* and *A. lumbricoides*. In addition, Anti-helminthic efficacy, measured by cure

¹⁸ Age, Date of Birth, Sex, Participant ID, Guardian relationship, age and contact details

²⁰ Vital signs should Include heart rate, respiration rate, body temperature and blood pressure.

¹⁴ Informed consent will be obtained from parents or guardians of all participants <18years. Informed consent/assent can be performed up to 3 months prior to screening visit as part of the pre-screening activities OR during screening visit

 $^{^{\}rm 15}$ Assent to participate in the trial will be obtained from participants 12-17 years old.

¹⁶ A stool collection kit will be provided to participants for the collection of stool samples after providing assent and consent. The stool should be collected <24 h before examination for eligibility check. An aliquot of the collected stool sample will be stored for QC by PCR to confirm microscopic results from Kato-Katz and Baermann test if microscopy positive at screening and for all follow-up stool samples. All samples will be tested at site. Should technical issues arise or in case of discrepancy in results, an aliquot of the stool sample will be tested abroad for QC purposes.

¹⁷ Lab tests will be performed on a fresh stool sample collected <24 hours before examination.

¹⁹ Physical exam should include clinical diagnosis of scabies (rush/lesions on skin) before and after treatment. During unscheduled visits Physical exam will be performed only if necessary.

²¹ A urine test kit will be provided in order to collect urine sample from all participants which will be examined by haematuria strip test as a proxy *for* Schistosoma eggs and to confirm negative pregnancy test for female participants \geq 12 years old or post-menarche.

²² Serum HIV test will be offered only to eligible participants at the Manhiça site in Mozambique because of high HIV prevalence.

²³ Treatment Day 0. For all participants in Arms 1, 2 and 3. Treatment dose will be given under direct supervision.

²⁴ Treatment Day 1. Only for participants in treatment Arm 3. Close observation for 3 hours post-treatment for safety evaluations.

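### FDCx3 children get three 3-hour post-dose watches against one in the other arms, and nominally two more days of follow-up; the adverse-event count models state no allowance for this, so a modest FDCx3 excess could be partly detection

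*SAP*

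**What the plan says.** **Watches.** Protocol section 3 (Primary outcome measures) states: "A close surveillance, 3 hours post-treatment, will be conducted each day a participant receives study treatment". SAP 2.2.1 repeats this. The footnotes to both Phase III schedules limit the later watches to one arm: "Treatment Day 1. Only for participants in treatment Arm 3. Close observation for 3 hours post-treatment for safety evaluations". The Day 2 footnote has the same form, and so do the Phase II footnotes.

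**Scheduled visits.** Adverse-event monitoring is marked for every arm on Days 0, 1, 2, 3 and 7 and at Visit 6 (Protocol 1.4 and 1.5; SAP Tables 1 and 2). Protocol 8.1 agrees: "Safety assessment of participants will occur from day 0 (visit 1) to day 3 (visit 4"), with further visits at Day 7 and Day 21.

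**End of follow-up.** The efficacy stool sample at the final visit is defined by "analysing a stool sample taken 21(+/-7) days after completing treatment" (SAP 2.2.1). Protocol 8.3.7 gives one duration for all arms: "The duration of the study is 21 (+/-7days").

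**Analysis.** TEAEs are "adverse events that occur or worsen on or after the first dose of study treatment" (SAP 5.5.1), with no end of window. On counts the SAP says: "For a count outcome such as the number of TEAEs or treatment-emergent SAEs incidence rate ratio (IRR) and its 95% CI will be computed", by Poisson or negative binomial regression. SAP 5.5 sets the comparisons: by arm, both FDC arms pooled, and number of FDC doses received. Protocol 6.3 (Blinding) leaves participants and safety assessors unblinded.

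**The concern.** More observation finds more events. A child in FDCx3 spends 9 hours under a physician's eye after dosing, against 3 hours in the other arms, and is followed from first dose for nominally two days longer. Mild background events in those extra hours and days add to the FDCx3 count even if the drug causes none of them. The dose-response comparison is the most exposed: each dose brings its own watch, so number of doses and number of watches are completely confounded.

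Safety is the Phase II primary endpoint and a Phase III secondary endpoint. The sample-size section of both documents asks whether the three-day regimen gains enough to be worth considering, and tolerability will weigh in that judgement. As the SAP stands, a rate ratio somewhat above 1 for FDCx3 or pooled FDC could not be divided between drug effect and detection.

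**Working it through.** The documents give no expected adverse-event rate for this trial, no rate ratio and no power for safety, so there is no stated figure to reproduce.

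**Inputs**
- Watch time: 3 h per dose, so 3 h for ALB and single-dose FDC and 9 h for FDCx3.
- Nominal follow-up from first dose (inferred): 21 days = 504 h, or 2 + 21 = 23 days = 552 h for FDCx3, whose last dose is on Day 2.
- Assumed: constant background hazard, no drug effect, every event in a watch recorded, and a fraction d recorded outside a watch. The documents give no value for d.

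**Time alone.** 23/21 = 1.095.

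**Time and watches, FDCx3 against ALB.** Ratio = (9 + d × (552 − 9)) / (3 + d × (504 − 3)). Multiplying by 21/23 leaves the part due to the watches.

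| d | Crude ratio | Watch part |
|---|---|---|
| 0.50 | 280.5 / 253.5 = 1.107 | 1.010 |
| 0.25 | 144.75 / 128.25 = 1.129 | 1.031 |
| 0.10 | 63.3 / 53.1 = 1.192 | 1.088 |

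**Pooled FDC against ALB.** Arm sizes over both phases, from the final sample-size table: ALB 26 + 251 = 277, FDC 50 + 419 = 469, FDCx3 50 + 427 = 477. Mean follow-up in pooled FDC is (469 × 21 + 477 × 23) / 946 = 22.0 days, a time ratio of 1.048. That is about half the distortion seen for FDCx3 alone.

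**Effect on a two-sided 5% test.** This was simulated with Poisson counts (200,000 runs, Wald test). The rate is 48/175 = 0.274 events per child, from the Honduras trial described in Protocol 2.2. Using that rate, and pooling the phases for safety, are both assumptions.

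| Null case, ALB 277 against FDCx3 477 | No offset | With offset |
|---|---|---|
| Time only | about 9.5% | 4.9% |
| d = 0.50 | 10.7% | 5.0% |
| d = 0.25 | 13.4% | 5.2% |
| d = 0.10 | 23.7% | 8.9% |

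For single-dose FDC against FDCx3 (469 against 477), time alone gives about 11.5%. With the Phase II sizes (26 against 50), rejection stays at 3.5% to 4.1% over the same range of d, so the issue there is interpretation of the estimate, not false significance.

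The sample-size text in both documents gives 427 for FDC and 419 for FDCx3 in Phase III, the reverse of the table sums (198 + 120 + 101 = 419; 198 + 119 + 110 = 427). The table sums are used here; the two should be reconciled.

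**The case against.** The strongest reply is that routine ascertainment is equal. Every arm is seen and asked about adverse events on the same days, and Protocol 8.3.3.1 lets participants and parents report events themselves. An event in an ALB child on Day 1 can be picked up at that day's visit or the next. This stands, and it is why the watch effect is small at reasonable detection rates.

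Four further replies have force:
- The two-day gap is inferred from the stool-sample timing. Protocol 8.3.7 does not mention it, and it is small beside a ±7-day visit window.
- An incidence rate ratio ordinarily implies person-time, so on duration the SAP is silent and not shown to be unadjusted.
- The extra watches follow extra doses, so part of any excess would be a real regimen effect.
- The stopping and progression rules (SAP 3.6) rest on serious adverse reactions and SUSARs. The rate ratio does not trigger them, and such events are unlikely to depend on a watch.

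A reader might infer something much stronger: that if a quarter or half of recorded events came to light only through a watch, FDCx3 would show a ratio near 1.5 or 2 by construction. Let f be the share of ALB events that owe their detection to the single watch. Under the constant hazard, f = 3(1 − d)/(3 + 501d). Then f of 10%, 25% and 50% needs d of about 5%, 1.8% and 0.6%. The last two mean that over 98% of events outside a watch are missed despite five further visits, and nothing in the documents suggests that. If events instead cluster after a dose because the dose caused them, they are not artefact.

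A reader might also point to Phase II pharmacokinetic samples: 20 of 50 FDCx3 children (four subgroups of five) have one 48 or 72 hours after the Day 2 dose, on Day 4 or 5. The schedule assigns no adverse-event assessment to those contacts, so they carry little weight.

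**Conclusion.** The point holds in a limited form. Three watches against one is explicit in both documents, the longer nominal follow-up is a fair inference, and SAP 5.5.1 states no offset, end of window or sensitivity analysis for either. A modest excess for FDCx3 or pooled FDC would therefore be ambiguous, and the trend by number of doses more so.

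Under a constant hazard, the watch effect is about 1.01 to 1.09 for d between 50% and 10%, and time adds at most 1.095. The true size cannot be known, because the documents give neither d nor a background rate. The rejection rates also rest on pure Poisson variation, while the SAP allows a negative binomial model, and on a rate from a trial that mixed regimens. They illustrate the direction and rough scale only. A large excess in FDCx3 could not plausibly be explained this way.

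**What to change.** Amend SAP 5.5.1 and keep the planned all-time tables.

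1. **Equal time.** Count TEAEs to a common cut-off from first dose in all arms, or state a log person-time offset. Set the cut-off late: with a Day 0 to 7 window, the ratio from the watches is 1.04 at d = 0.50 and 1.28 at d = 0.10. The offset assumes a constant hazard. If most events fall soon after dosing, it could over-correct FDCx3 by up to 21/23 = 0.913.
2. **Equal watches.** Add a supportive comparison of the pooled FDC arms against ALB for TEAEs with onset within 24 hours of the Day 0 dose and before any Day 1 dose. All arms then have one watch, and both FDC arms have had the same treatment. It is cleanest in Phase III, because Phase II pharmacokinetic contacts on Day 0 occur in the single-dose arms but not in FDCx3.
3. **Bounds.** Report the FDCx3 rate ratio with and without TEAEs with onset within 3 hours after the Day 1 and Day 2 doses, labelled as upper and lower bounds. The excluded events include real acute effects of doses 2 and 3, so the lower figure is not a corrected estimate.

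The cost is a few sentences and some extra table columns; Protocol 8.3.3.1 and 8.3.4 already require onset time. Two limits remain. The Day 0 window says nothing about doses 2 and 3, and onset time does not show that an event was found only because of the watch.
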